Dose Modification of copanlisib is described in Section 6.6.

Duration of Treatment:

Patients will be treated until one of the following events: disease progression, unacceptable adverse event(s), withdrawal of consent, general or specific changes in the patient's condition that render the patient unacceptable for further treatment in the judgment of the investigator.

Sample Size and Statistical Consideration:

The study will enroll 42 patients. The two arms will enroll patients in parallel and independently. Safety analysis will be done by pooling patients from the two arms together. Efficacy analysis will be conducted independently within each of the two arms (lymphoma, solid tumor).

Patients who do not complete the planned cycle 2 cycles of treatment, which is required for the first evaluation of response, will be replaced.

(a) The lymphoma arm will enroll 23 patients with FL.

- Simon's two-stage design (Simon, 1989) will be used. The null hypothesis that the true ORR rate is 41% will be tested against a one-sided alternative. In the first stage, 13 patients will be accrued. If there are 5 or fewer ORRs (**To be assessed after completing 4 cycles of the treatment**) in these 13 patients, the study will be stopped for futility. Otherwise, 10 additional patients will be accrued for a total of 23. The null hypothesis will be rejected if 14 or more ORRs are observed in 23 patients. This design yields a type I error rate of 5% and power of 80% when the true ORR rate is 67%. Assuming that the CR rate is 0.09 (2 out 23), with 23 subjects we will have 80% power to claim that the true CR is at least 30%.
- The reference range of ORR in FL is 40% (n = 16. Dreyling et al, Ann Oncol. 2017) to

59% (n = 104. Dreyling et al, J Clin Oncol. 2017).

• The reference CR rate is 14% (n = 104. Dreyling et al, J Clin Oncol. 2017).

(b) The solid tumor arm will enroll 19 patients with EC.

Simon's two-stage design (Simon, 1989) will be used. The null hypothesis that the true ORR rate is 0.10 will be tested against a one-sided alternative. In the first stage, 11 patients will be accrued. If there are 1 or fewer ORRs (To be assessed after completing 4 cycles of treatment) in these 11 patients, the study will be stopped for futility. Otherwise, if >=2/11 responses are observed, then 8 additional patients will be accrued for a total of 19. The null hypothesis will be rejected if 4 or more ORRs are observed in

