19 patients. This design yields a type I error rate of 10% and power of 81% when the true ORR rate is 30%.

Safety:

Patients will be monitored carefully for the development of adverse events (AEs). AE will be evaluated according to criteria outlined in the National Cancer Institute (NCI) Common Terminology Criteria for Adverse Events (CTCAE), version 5.

Safety Trigger

There will be ongoing safety monitoring.

Interim safety analysis will be performed upon enrollment of 12 and 24 subjects. Safety analysis will be done by pooling patients from the two arms together.

The safety trigger will be activated if any of the following Safety Trigger Events (STE) happens during the first cycle of treatment:

- During the interim analysis of the first 12 subjects: 3 incidents of STE excluding mortality, or 2 incidents of mortality deemed not likely to be due to progression of the cancer but possibly related to the treatment. The study will be stopped.
- During the interim analysis of the first 24 subjects: 5 incidents of STE excluding mortality, or 3 incidents of mortality deemed not likely to be due to progression of the cancer but possibly related to the treatment. The study will be stopped.

Safety Trigger Events (STE) will defined as the following:

- Any non-hematologic toxicity grade 3-4 that require delay of treatment by more than 7 days despite optimal management.
 - Note that a patient who experiences a STE may be allowed to continue the study, as long as the patient can safely resume therapy within 21 days.
- Any hematologic toxicity grade 3-4 that require delay of treatment by more than 7 days despite optimal management including blood products and growth factors.
 - Note that a patient who experiences a STE may be allowed to continue the study, as long as the patient can safely resume therapy within 21 days.

• Any mortality.

Efficacy Outcome:

Patients will be monitored for clinical and/or radiographic evidence of disease response. Response will be evaluated using clinical parameters, CT or PET/CT scan (PET/CT scan is preferred), and bone marrow or other tissue biopsy (when applicable for lymphoma), according to the Updated Recommendations for Evaluation, Staging, and Response Assessment for Hodgkin and Non-Hodgkin Lymphoma: The Lugano Classification. For solid tumor the response will be determined in accordance with the revised Response Evaluation Criteria in Solid Tumors

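### The safety trigger does not say whether cycle 1 grade 3-4 toxicity that ends treatment permanently without a hold counts as a non-fatal event

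*Combined protocol and SAP*

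**What the plan says.** Under Safety Trigger, the synopsis pools the two arms and sets two looks: "Interim safety analysis will be performed upon enrollment of 12 and 24 subjects". The study stops at 3 non-fatal STEs (or 2 qualifying deaths) in the first 12 patients, or 5 non-fatal STEs (or 3 qualifying deaths) in the first 24. Only the first cycle counts.

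Three events are listed:

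- "Any non-hematologic toxicity grade 3-4 that require delay of treatment by more than 7 days despite optimal management"
- "Any hematologic toxicity grade 3-4 that require delay of treatment by more than 7 days despite optimal management including blood products and growth factors"
- "Any mortality"

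Under each of the two non-fatal events, a note says that a patient with an STE "may be allowed to continue the study, as long as the patient can safely resume therapy within 21 days".

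Two other places bear on the point. Duration of Treatment reads: "Patients will be treated until one of the following events: disease progression, unacceptable adverse event(s), withdrawal of consent", followed by changes in the patient's condition. The text that closes the part on laboratory criteria for dosing treats a delay of more than 2 days as a missed dose, starts a new cycle after 8 to 21 days, and removes a patient whose dose is delayed by more than 21 days. It refers to Section 5.6 for withdrawal criteria and Section 6.6 for dose modification. Neither section is in the public text.

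**The concern.** A delay of more than 7 days is a necessary part of both non-fatal definitions. No available part of the document lists permanent discontinuation for toxicity as an STE, while an unacceptable adverse event is a reason of its own for ending treatment. If an investigator stops treatment for good in response to a grade 3-4 toxicity, without first holding a dose, no dose has been delayed. Taken literally, that patient is not an STE, whereas a patient who resumes after 8 days is.

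The STE count, with its separate limits on deaths, is the only numerical safety boundary. The ongoing safety monitoring that the synopsis mentions has no stated threshold. Such a patient also leaves the response analysis: patients who do not complete two cycles are replaced, and response evaluability requires one completed cycle. The patient stays evaluable for toxicity after one dose, but that analysis carries no stopping limit.

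With limits of 3 and 5, the classification of one patient can decide whether the study stops. If two careful readers can classify the same withdrawal differently, the rule is not fully specified in advance, and the question will be settled after the event is known.

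**Working it through.** **Which routes out of treatment are counted.** Take a grade 3-4 toxicity in cycle 1:

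| Course | Delay over 7 days? | Non-fatal STE? |
|---|---|---|
| Dosing held, resumed after 8 days | Yes | Yes |
| Dosing held, no recovery, removed after 21 days | Yes (21 > 7) | Yes |
| Treatment stopped permanently, no hold | No dose was postponed; or the delay is indefinite | Not stated |

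The continuation note does not settle the third row. It says what may happen to a patient who is already an STE, and does not make discontinuation an STE. It does show that the authors expected some STE patients never to resume.

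The word delay is also used in two ways. In the dosing text, anything over 2 days is a missed dose; in the STE bullets, the threshold is more than 7 days. If the day 8 dose is missed and dosing takes place on day 15, the gap is 15 − 8 = 7 days, which is not more than 7.

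**Scale.** The document states no acceptable STE rate and no stopping probability for this rule, so there is no figure to reproduce. The calculation below is illustrative.

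Inputs from the synopsis: looks at 12 and 24 patients; non-fatal limits 3 and 5.

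Assumptions: at most one non-fatal STE per patient; independent patients; the same event probability p for all; deaths ignored.

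Let X be the count in the first 12 patients and Y the count in the next 12, each Binomial(12, p). The trigger is not activated if X ≤ 2 and X + Y ≤ 4, so

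P(trigger by 24) = 1 − Σ over x = 0, 1, 2 of P(X = x) × P(Y ≤ 4 − x).

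For p = 0.10:

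- x = 0: 0.2824 × 0.9957 = 0.2812
- x = 1: 0.3766 × 0.9744 = 0.3669
- x = 2: 0.2301 × 0.8891 = 0.2046
- Sum = 0.8527, so P(trigger) = 1 − 0.8527 = 0.1473

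Now assume that 10% of patients have a delay-type STE, and that a further share d are stopped permanently in cycle 1 for grade 3-4 toxicity without a hold. If those are not counted, the counted rate stays at 10%. If they are counted, it is 10% + d:

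| d (assumed) | Rate if counted | Trigger, not counted | Trigger, counted | Difference (points) |
|---|---|---|---|---|
| 1% | 11% | 14.7% | 18.6% | 3.9 |
| 2% | 12% | 14.7% | 22.9% | 8.2 |
| 5% | 15% | 14.7% | 37.3% | 22.6 |
| 10% | 20% | 14.7% | 61.4% | 46.7 |

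The direction does not depend on the assumed rates: leaving out events can only lower the chance of triggering. The size depends almost entirely on d, which the document does not give.

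**The case against.** The strongest answer is that the bullets ask whether the toxicity requires a delay of more than 7 days, not whether a late dose was eventually given. A toxicity so severe that dosing can never resume can naturally be read as requiring an indefinite delay, and so as an STE. That reading is available, and it means that the text is silent on the event and does not clearly exclude it. It does not remove the ambiguity, because the dosing text uses delay for a dose that is given later or missed, which differs from ending treatment.

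A reader might infer more than the document supports:

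- That treatment-ending toxicity in general escapes the trigger. It does not. The usual route, a hold without recovery, passes 7 days and is counted.
- That Duration of Treatment contradicts the STE bullets. It is a general list of reasons for ending treatment and says nothing about timing. It leaves room for a stop without a hold, but does not say that one occurs.
- That a more toxic regimen would give a lower count. The calculation holds delay-type events fixed and adds discontinuations, so the count never falls. A lower count would need holds to be replaced by immediate stops, which was not modelled.
- That 15% against 61% is the size of the problem. It is the upper end of an assumed range. At 1% or 2%, the change is about 4 or 8 points.

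It also stands that Sections 5.6 and 6.6 may say whether withdrawal for toxicity normally follows a hold. They could not be checked.

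**Conclusion.** The point holds in a limited form. The STE definitions leave open whether a cycle 1 grade 3-4 toxicity counts when it stops treatment permanently with no hold. Toxicity that holds dosing beyond 7 days and then ends treatment is already counted.

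In the illustration, the gap is worth between 3.9 points (1% immediate discontinuations) and 46.7 points (10%) in the chance of triggering, from a base of 14.7%. This rests on an assumed 10% rate of delay-type events, on the assumed discontinuation rates, on one event per patient, and on the literal reading under which none of the immediate stops is counted. None of these rates comes from the document. The case for acting rests on the ambiguity in the only numerical safety stop, and not on any one of these figures.

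**What to change.** In both non-fatal STE bullets, count a cycle 1 grade 3-4 toxicity that either delays treatment by more than 7 days or leads to permanent discontinuation of study treatment because of that toxicity. Make the wording consistent with Duration of Treatment, with the dosing text on delayed and missed doses, and with Sections 5.6 and 6.6. This changes only what the study-level rule counts. Clinical decisions to stop a patient are untouched.

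The drafting cost is one phrase in the protocol and in any safety monitoring plan. The real cost is that the trigger becomes more likely to fire, by an amount that depends on how often treatment is stopped without a hold. At 1% to 2% this is small; at 5% to 10% it changes the rule materially. The sponsor should therefore state the operating characteristics of the 3-of-12 and 5-of-24 limits under the revised definition, over a plausible range of event rates, and confirm that the limits are still the ones it intends.

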The Phase II study will enroll 42 patients in two study groups. The lymphoma study group will enroll 23 patients with FL, and the solid tumor group will enroll 19 patients with EC.

In cycle 1, patients will first start ketogenic diet for 7 days (Day -6 to Day 0). Only patients who demonstrate compliance and tolerance with the ketogenic diet for all 7 days during the run-in

phase, as confirmed by pertinent blood and urine tests, will be allowed to continue the study and treatment using copanlisib and the ketogenic diet starting on day 1. In cycle 2 and beyond, patients will start the ketogenic diet and copanlisib on day 1.

Treatment Plan:

- Copanlisib: Copanlisib will be infused intravenously on days d1, 8, 15 of each cycle, over 1 hour, of 28-day cycles.
- Ketogenic diet:
 - Prior to the first treatment patients will start the ketogenic diet for 6 days (Day -5 to Day 0). Patients who demonstrate compliance and tolerance with the ketogenic diet, as confirmed by pertinent blood and urine tests and recorded dietary intake, will be allowed to continue the study and start copanlisib on Day 1. The ketogenic diet will continue daily throughout the treatment days.
 - In cycle 2 and beyond, patients will start the ketogenic diet and copanlisib on day 1. The ketogenic diet will then continue daily throughout the treatment days.
 - All patients will be eligible to receive the ketogenic diet as long as the patients remain on the trial. If patients want to remain on the trial to receive Copanlisib but wish to discontinue the ketogenic diet, they should do so at the following time: (a) when they have achieved a complete response, or (b) when they have completed 4 cycles of treatment. In the rare case when a patient wants to discontinue the ketogenic diet after having completed only 2 or 3 cycles of therapy but having not achieved a CR, the patient will be allowed to remain in the study and receive copanlisib without having to take the ketogenic diet. However, if a patient wishes to stop the ketogenic diet before

cycle 2 is completed, when the response will be first evaluated, the patient will not be allowed to continue this trial but will be replaced.

REGIMEN DESCRIPTION					
Agent	Premedications/Precautions	Dose	Route	Cycle Length	
Copanlisib	IV Hydration (Normal Saline 500 cc IV in 30 minutes after copanlisib infusion)	60 mg	IV over 60 minutes	28 days	
Ketogenic diet		Three times daily	Oral, three times daily		

Dose Modification:

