(RECIST) guideline. CT or PET/CT scan will be performed after every two 28-day cycles of. After cycle 4, if the patient has achieved CR, scans will be done every 3 cycles.

Data analysis:

All patients receiving at least one dose of copanlisib will be evaluable for toxicity and all patients completing at least one 28-day cycle of therapy (copanlisib plus ketogenic diet) will be evaluable for response and time-to-endpoint analyses.

Response will be estimated with exact 95% confidence intervals (CIs). We will estimate overall survival, progression-free survival, and duration of response using the Kaplan-Meier method. Group comparisons, between groups associated with different biomarkers described below, will be made using a two-sided log-rank test, and the estimated hazard ratios and 95% CIs will be calculated using Cox regression. Overall survival will be assessed post hoc in the trial patients. In the exploratory correlative biomarker analyses, any patients with assessable biological samples (blood, tumor etc) will be included. An association between disease outcome (complete response, partial response, stable disease, progression of disease, duration of response, and progression-free survival) and changes from baseline in biomarker concentrations as a function of treatment over time will be assessed. Because of sample size considerations, we will base group comparisons for these analyses on two-sample t test. We will do correlative studies including all enrolled patients that have adequate biological samples available for analysis. We plan to assess changes over time and estimate odds ratios using mixed-effects logistic regression models or a linear model if the sample sizes for comparison are too small. We will summarize continuous variables as means and SDs, and categorical variables as counts with percentages. We will not do multiple testing adjustments. All the analyses will be done with SAS version 9.4.

Study Rationale

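### The toxicity set opens at the first copanlisib dose, so patients stopped in the ketogenic-diet run-in fall outside it and diet intolerance before Day 1 is under-reported

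*Combined protocol and SAP*

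**What the plan says.** Under Data analysis, the Protocol Synopsis defines the toxicity set: "All patients receiving at least one dose of copanlisib will be evaluable for toxicity". The same sentence describes the therapy as both components when it defines the response set: "all patients completing at least one 28-day cycle of therapy (copanlisib plus ketogenic diet) will be evaluable for response". The Regimen Description table also gives the diet its own row beside copanlisib.

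The diet comes first. The text under Study flow chart places a run-in inside cycle 1 and restricts who may proceed: "Only patients who demonstrate compliance and tolerance with the ketogenic diet for all 7 days during the run-in". The Treatment Plan repeats the condition; those who meet it "will be allowed to continue the study and start copanlisib on Day 1".

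The two places differ on length. Study flow chart has 7 days, Day -6 to Day 0. The Treatment Plan says "Prior to the first treatment patients will start the ketogenic diet for 6 days", which it gives as Day -5 to Day 0.

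The Safety section promises adverse-event monitoring by CTCAE version 5 without a dosing condition. Under Safety Trigger, the interim looks are timed by enrolment of 12 and 24 subjects and concern first-cycle events. Non-fatal trigger events are grade 3-4 toxicities that delay treatment by more than 7 days; any death is also a trigger event.

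**The concern.** Entry to the toxicity set depends on having got through the first week of one of the two interventions under study. A patient who starts the diet, has an adverse event on it and is stopped before Day 1 has been exposed to study therapy, yet contributes neither an event nor a denominator to the planned toxicity analysis.

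At stake is the description of the combination's safety. The reported figures would apply to patients already shown to manage the diet. A reader deciding whether the regimen is tolerable would not see how many people failed at the diet stage, or why. The only listed objective on diet uptake is compliance, which would record that patients did not follow the diet but not what harm they had.

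**Working it through.** The plan gives no figure that depends on this set, so there is nothing to reproduce. The check traces a patient through the rules and then shows what can and cannot be said about size.

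**Step 1. Trace the patient.**
- Diet begins on Day -6 or Day -5 (Study flow chart; Treatment Plan).
- Compliance and tolerance are required before copanlisib on Day 1 (both places).
- A patient who fails this condition has zero copanlisib doses.
- Toxicity evaluability requires at least one dose (Data analysis), so this patient is not in the set.
- The text available defines no other safety set. In the same section, correlative studies are opened to all enrolled patients with adequate samples, so the toxicity set is the narrower of the two.

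The rule does not remove run-in events in patients who later receive copanlisib.

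**Step 2. How many could be absent.** Planned enrolment is 42 (23 + 19). Assume 42 patients are dosed and a fraction f of diet starters fails the run-in; f is an assumption. Starters N = 42/(1 - f), rounded up.
- f = 0.10: 42/0.90 = 46.7, so N = 47 and 47 - 42 = 5 absent.
- f = 0.20: 42/0.80 = 52.5, so N = 53 and 53 - 42 = 11 absent.

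**Step 3. Effect on a pooled grade 3-4 rate.** Let x be the dosed patients with a grade 3-4 event and k the run-in failures with one. The plan reports x/42; a diet-started set would report (x + k)/N. Take N = 50 (8 failures) for illustration:

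| x | Plan: x/42 | k = 0 | k = 4 | k = 8 |
|---|---|---|---|---|
| 8 | 19.0% | 16.0% | 24.0% | 32.0% |
| 21 | 50.0% | 42.0% | 50.0% | 58.0% |
| 30 | 71.4% | 60.0% | 68.0% | 76.0% |

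The pooled rate rises only when k/(N - 42) exceeds x/42. With k = 4 the break-even is 4/8 = 50% in dosed patients. The documents give neither x nor k, so neither direction nor size is established for the pooled rate. What does not depend on x is the omission itself: with k = 4, four of 50 starters (8%) had a grade 3-4 event that the toxicity analysis would not show.

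**Step 4. The first safety look.** The non-fatal threshold is 3 events in 12 subjects. The plan does not say whether run-in failures are among the 12 or whether their events count. Assume a trigger-event rate s = 5% in dosed patients and a further fraction q of starters with a run-in event treated as a trigger event. Then p = q + (1 - q)s, and the chance of reaching the threshold is 1 - Σ C(12, j) p^j (1 - p)^(12 - j) over j = 0, 1, 2.
- 12 dosed patients, run-in ignored: p = 0.05, chance 2.0%.
- q = 5%: p = 0.0975, chance 10.5%.
- q = 10%: p = 0.145, chance 24.7%.
- q = 20%: p = 0.24, chance 57.8%.

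These figures show only that the counting rule matters. Whether a run-in event can qualify is itself unclear, since a patient who never starts copanlisib does not plainly have a treatment delay.

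**The case against.** The other side has several fair points.

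- The Data analysis sentence says all dosed patients are evaluable; it does not say that no one else is. Still, it is written as the definition of who is evaluable for each purpose, and restriction is the ordinary reading.
- The Safety section monitors patients without a dosing condition, times its looks by enrolment and counts any first-cycle death. Since Study flow chart places the run-in in cycle 1, a run-in death may reach the trigger. This stands as an ambiguity. It concerns collection and stopping, and does not put run-in failures back into the toxicity analysis. A reader might infer that run-in adverse events go unrecorded; the documents do not say so.
- The exclusion criteria already screen out some patients at diet-related risk, such as those with BMI below 20, nephrolithiasis, the listed food allergies or intolerances, or triglycerides above 300 mg/dL. Severe run-in events may therefore be few, and the case k = 0 in the table is a real possibility.
- Toxicity among patients who received both components is a legitimate quantity. No primary or secondary objective concerns toxicity, and neither Simon rule uses this set. That argues for keeping the dosed set as a second table, not as the only one.
- Only synopsis text is available. Sections 5.6 and 6.6, which it cites, could not be checked.

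Three stronger readings are tempting and not supported. A reader might infer that the four events among 50 starters in Step 3 add 8 points to the grade 3-4 rate; the denominator changes too, and the table shows that the rate can rise, stay level or fall. A reader might infer that those left out are precisely the diet-intolerant; non-compliant patients and any kept from dosing by the Day 1 laboratory criteria are left out as well. A reader might infer that all early diet harms are lost; events in patients who go on to copanlisib are not excluded.

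**Conclusion.** The concern holds in a limited form. Taken together, the run-in condition and the evaluability rule leave patients stopped for diet intolerance before Day 1 outside the planned toxicity analysis, although the diet is study therapy. Pre-Day 1 diet intolerance is therefore under-reported.

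The number affected is unknown. The range of about 5 to 11 absent starters rests on assumed run-in failure of 10% to 20% and 42 dosed patients. A general statement that the combination's overall toxicity rate is biased towards looking safe is not supported, because the direction depends on rates the documents do not give. The efficacy designs are unaffected. The matter should be corrected, mainly because the remedy is cheap and the handling of run-in patients at the safety looks is also unstated.

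**What to change.** - Define the toxicity population as all patients who start the ketogenic diet, from the first run-in day.
- Tabulate adverse events in the run-in separately from those after the first copanlisib dose.
- Keep the copanlisib-dosed set as a second table.
- Report the number of run-in failures with reasons: intolerance, non-compliance, Day 1 laboratory criteria, other.
- State under Safety Trigger whether run-in patients count among the 12 and 24 subjects, and whether run-in events, including deaths, count toward the thresholds.
- Reconcile the 7-day and 6-day run-in statements, since they fix when the observation window opens.

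The cost is wording and one extra table. These patients are already on study and having blood and urine tests in the run-in, so no added patients or visits are needed.

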As we recently reported ketogenic diet can suppress hyperinsulinemia associated with PI3K inhibitors, leading to potentiation of the anti-tumor effects of PI3K inhibitors[79]. Copanlisib potently inhibits PI3K α and PI3K δ . It has been approved for the treatment of relapsed follicular lymphoma, based on ORR of 59% (84 of 142 patients)[83]. The CR rate in FL was 14%, and the median progression-free survival was 11.2 months. Copanlisib demonstrated encouraging clinical activity in marginal zone lymphoma (ORR 70% including 9% CR). While these results are clinically meaningful, FL and MZL inevitably develop resistance to copanlisib with time, even in those patients who initially respond to the therapy. Novel strategies to improve the efficacy of copanlisib in FL and MZL, by improving CR and PFS, may transform how we manage these incurable malignancies.

Interestingly, copanlisib has also demonstrated clinical activity in aggressive lymphomas in a smaller study of heavily pre-treated patients[84]. Objective responses were achieved in patients with DLBCL (one PR; ORR 6.7%), PTCL (two CRs, one PR; ORR 21.4%), MCL (two uCRs, five PRs; ORR 63.6%), and transformed FL (both PRs; ORR 33.3%). These results suggest that copanlisib warrants further investigation in aggressive lymphomas such as PTCL and DLBCL. In a Phase I study of both solid tumors and lymphoma, sixteen of 20 patients treated at the MTD had reduced ⁽¹⁸⁾FDG-PET uptake; 7 (33%) had a reduction >25%. One patient achieved a complete response (CR; endometrial carcinoma exhibiting both PIK3CA and PTEN mutations and complete PTEN loss) and two had a partial response (PR; both metastatic breast cancer). Among the nine NHL patients, all six with follicular lymphoma (FL) responded (one CR and five PRs) and one patient with diffuse large B-cell lymphoma had a PR by investigator assessment; two patients with FL who achieved CR (per post hoc independent radiologic review) were on treatment >3 years.

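### PFS is to be estimated only in patients who completed cycle 1, so deaths and clinical progressions during that cycle drop out of the Kaplan-Meier curve; the OS population is unclear

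*Combined protocol and SAP*

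**What the plan says.** All places cited are in the Combined protocol and SAP.

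- **Efficacy set (Data analysis).** "all patients completing at least one 28-day cycle of therapy (copanlisib plus ketogenic diet) will be evaluable for response and time-to-endpoint analyses".
- **Safety set (same sentence).** "All patients receiving at least one dose of copanlisib will be evaluable for toxicity". This wider set is used for toxicity only.
- **Estimation (Data analysis).** "We will estimate overall survival, progression-free survival, and duration of response using the Kaplan-Meier method". No time origin, censoring rule or sensitivity analysis is given there.
- **Overall survival (Data analysis).** "Overall survival will be assessed post hoc in the trial patients". Who these patients are is not defined further.
- **Replacement (Sample Size and Statistical Consideration).** "Patients who do not complete the planned cycle 2 cycles of treatment, which is required for the first evaluation of response, will be replaced". No exception is made for death or progression. Under Treatment Plan, a patient who stops the diet before the end of cycle 2 is handled likewise: "the patient will not be allowed to continue this trial but will be replaced".
- **End of treatment (Duration of Treatment).** Progression and unacceptable toxicity are both reasons to stop.
- **Scans (Efficacy Outcome).** Imaging follows every second 28-day cycle, so the first scheduled scan comes after cycle 2.
- **Background (Study Rationale).** For copanlisib alone, "the median progression-free survival was 11.2 months".

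**The concern.** Membership of the PFS set depends on something that happens after treatment starts. Progression ends treatment, and death obviously does, so a patient with either event in cycle 1 cannot complete the cycle and cannot enter the curve. Everyone who does enter is known to have survived the first 28 days, and in practice to have had no recognised progression in them. If the clock starts at first dose, those 28 days count as event-free follow-up that was guaranteed by selection.

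At stake is the credibility of the PFS curve. The Study Rationale presents better PFS as one aim of adding the diet, and a single-arm trial invites readers to look at published figures. There is also an inconsistency within Data analysis. The exploratory biomarker work relates markers to PFS in any patient with usable samples, so two PFS populations could end up in the same report. Changing the ORR denominator would not settle this, because PFS and OS need their own population and time zero.

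**Working it through.** The plan gives no target, event count or power for PFS or OS, so there is no figure of its own to reproduce. The check is of the size of the distortion.

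**Inputs from the documents:** 23 FL and 19 EC patients; a 28-day cycle; a median PFS of 11.2 months (Study Rationale). **Assumed:** time from first dose; EC medians of 3 to 6 months, since the documents give no PFS for EC; constant hazard in step 2 only.

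**1. Without a survival model.** Suppose k of N dosed patients fail in cycle 1 and nobody is censored in that cycle. After day 28 the all-treated curve equals (N − k)/N times the curve in the remaining patients. Dropping the k failures therefore multiplies later values by N/(N − k).

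| N | k | Factor | A true 50% reads |
|---|---|---|---|
| 23 | 1 | 23/22 = 1.045 | 52.3% |
| 23 | 2 | 23/21 = 1.095 | 54.8% |
| 23 | 3 | 23/20 = 1.150 | 57.5% |
| 19 | 1 | 19/18 = 1.056 | 52.8% |
| 19 | 2 | 19/17 = 1.118 | 55.9% |
| 19 | 3 | 19/16 = 1.188 | 59.4% |

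If the k failures are replaced, so that N are analysed out of N + k dosed, the factor is (N + k)/N. For k = 2 that is 25/23 = 1.087 (50% reads 54.3%) or 21/19 = 1.105 (55.3%). With k = 0 every factor is 1 and there is no bias.

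**2. Under constant hazard.** Let c = 28/30.44 = 0.92 months and m be the true median.

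- Share with an event by day 28: 1 − exp(−ln 2 × c/m).
- Curve in those event-free at c: S(t)/S(c). Setting this to 0.5 gives a reported median of m + c.

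| m (months) | Event by day 28 | Reported median | Excess | 6-month PFS, true → reported |
|---|---|---|---|---|
| 11.2 (FL illustration) | 5.5%, about 1.3 of 23 | 12.1 | 8.2% | 69.0% → 73.0% |
| 6 (EC, assumed) | 10.1%, about 1.9 of 19 | 6.9 | 15.3% | 50.0% → 55.6% |
| 4 (EC, assumed) | 14.7%, about 2.8 of 19 | 4.9 | 23.0% | 35.4% → 41.5% |
| 3 (EC, assumed) | 19.1%, about 3.6 of 19 | 3.9 | 30.7% | 25.0% → 30.9% |

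Step 2 is an upper-end illustration. Constant hazard places progressions in the first 28 days, whereas scheduled imaging cannot find any until after cycle 2. The events actually lost would be deaths, clinical progressions and anything seen on an unscheduled scan.

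**3. Against sampling error.** With 23 uncensored exponential events, an approximate 95% interval around 11.2 months is 11.2 × exp(±1.96/√23), or 7.4 to 16.9 months. A shift of 0.92 months lies well inside it.

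**The case against.** The strongest reply is that little depends on these curves. PFS and OS appear in none of the primary, secondary or exploratory objectives, no decision rule uses them, and in FL the illustrated shift is small beside the sampling error. The scan schedule means few PFS events would be recorded in cycle 1. All of this stands, and it limits the severity. It does not remove the selection: sampling error is no defence of a one-directional bias that wording can avoid.

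Some stronger readings are tempting but not supported:

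- *OS is restricted in the same way.* The general rule covers time-to-endpoint analyses, but the separate OS sentence may intend a wider set. It neither defines one nor overrides the rule. The supportable statement is that the OS set is ambiguous.
- *Early treatment-related deaths are concealed.* They are not. Every dosed patient is in the toxicity set, and first-cycle deaths feed the safety trigger; at the interim on 12 subjects one stopping limit is "2 incidents of mortality deemed not likely to be due to progression of the cancer but possibly related to the treatment". Such deaths are missing from the PFS curve, not from the trial's reporting.
- *Every exclusion inflates PFS.* Stopping for toxicity or leaving because of the diet is not itself a PFS event. The direction of the effect of dropping those patients is uncertain.
- *A planned comparison with 11.2 months is invalidated.* No such comparison is planned; the figure is background. The documents do not show the cited study's analysis set, and it is not clear whether the figure refers to FL alone or to all indolent lymphoma in that study.
- *PFS is overstated whatever happens.* This requires at least one cycle-1 failure and a clock that starts at or before first dose. No origin is stated in the text available, which refers to protocol sections not included in it, so the lack of a definition here does not prove that none exists.

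**Conclusion.** The point holds for PFS. Applied as written, the rule removes cycle-1 deaths and clinical progressions from the Kaplan-Meier estimate, and the bias is upward if time runs from first dose and any such failures occur. For OS, the finding is only that the population needs to be stated.

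The size cannot be known in advance. Two lost failures in an arm would add about 5 to 6 percentage points to a true 50%, assuming no early censoring. The model-based figures (about 0.9 months on the median, 8% in relative terms at 11.2 months and 15% to 31% at assumed EC medians of 6 to 3 months) rest on constant hazard and should be read as upper-end. Because neither endpoint is a listed objective and the ORR decision does not depend on them, the severity is minor to moderate.

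**What to change.** Amend Data analysis to state that:

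1. PFS and OS are estimated in all patients who received any copanlisib, which is the toxicity set already defined, including patients later replaced.
2. Time runs from Cycle 1 Day 1.
3. Deaths and documented clinical progressions count as PFS events. Patients who leave without an event are censored at last assessment for PFS and at last contact for OS.
4. The one-cycle set is kept as a sensitivity analysis. Duration of response stays in responders.

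The sentence on OS should name the same set, so that only one reading is possible.

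The cost is an SAP wording change, slightly less favourable estimates, and collection of survival status for patients who leave early. Patients who leave before the first scan without an event will be censored very early and will add little information on PFS. Sample size, the Simon boundaries and treatment are unaffected.
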